12.6.1.3. Other Adverse Events

The following events require reporting to the sponsor (or designee) within 24 hours of learning of the event:

Pregnancy

Should a pregnancy occur, it must be reported and recorded on the sponsor's pregnancy form. Pregnancy in itself is not regarded as an AE unless there is a suspicion that an investigational product may have interfered with the effectiveness of a contraceptive medication.

Although pregnancy is not considered an AE, it is the responsibility of the investigator to report to the sponsor (or designee) by telephone within 24 hours of identification, any pregnancy occurring in a female participant or female partner of a male participant, during the study or within 120 days of the last dose of study treatment. Any complication of pregnancy affecting a female study participant or female partner of a male study participant, and/or fetus, and/or newborn must be reported as an SAE.

The outcome of all pregnancies (spontaneous miscarriage, elective termination, normal birth, or congenital abnormality) must be followed up and documented even if the participant was discontinued from the study.

Overdose of Study Treatment

Any accidental or intentional overdose over the intended dose of study treatment within the intended therapeutic window, if associated with an AE, should be reported within 24 hours.

Adverse Events of Special Interest

Adverse events of special interest (AESIs) must be reported within 24 hours of identification. Adverse events of special interest in this study include:

- Anaphylactic reactions or acute allergic reactions that require immediate treatment
- Severe injection site reactions that last longer than 24 hours
- Any severe infection, any bacterial infection requiring treatment with parenteral antibiotics or treatment with oral antibiotics for longer than 2 weeks, any clinical endoparasitosis, any opportunistic infection, any viral infection requiring antiviral treatment
- Note: Generally, all uncommon, atypical, peculiar, or unusually persistent infections, especially viral infections, should be reported as AESI.

Refer to the study manuals for the procedures to be followed.

12.6.1.4. Abnormal Laboratory, Vital Signs, or Electrocardiogram Results

The criteria for determining whether an abnormal objective test finding should be reported as an AE include:

- the test result is associated with accompanying symptoms; and/or
- the test result requires additional diagnostic testing or medical/surgical intervention; and/or
- the test result leads to discontinuation from the study, significant additional concomitant drug treatment, or other therapy.

Contact the medical monitor in the event the investigator feels that an abnormal test finding should be reported as an AE, although it does not meet any of the above criteria.

Repeating an abnormal test, in the absence of any of the above conditions, does not constitute an AE. Any abnormal test result that is determined to be an error does not require reporting as an AE.

12.6.2. Relationship to Study Drug

An investigator who is qualified in medicine must make the determination of relationship to the investigational product for each AE (Unrelated, Possibly Related or Probably Related). The investigator should decide whether, in his or her medical judgment, there is a reasonable possibility that the event may have been caused by the investigational product. If no valid reason exists for suggesting a relationship, then the AE should be classified as “unrelated.” If there is any valid reason, even if undetermined, for suspecting a possible cause-and-effect relationship between the investigational product and the occurrence of the AE, then the AE should be considered “related.”

If the relationship between the AE/SAE and the investigational product is determined to be “possible” or “probable” the event will be considered to be related to the investigational product for the purposes of expedited regulatory reporting.

12.6.3. Recording Adverse Events

Adverse events spontaneously reported by the participant and/or in response to an open question from the study personnel or revealed by observation will be recorded during the study at the

investigational study center. Clinically significant changes in laboratory values, blood pressure, and pulse need not be reported as AEs. However, abnormal values that constitute an SAE or lead to discontinuation of administration of study treatment must be reported and recorded as an AE. Information about AEs will be collected from the signing of the consent form until 30 days following the last dose of study treatment. Serious AE information will be collected from signing of the consent form until 30 days following the last dose of study treatment. The AE term should be reported in standard medical terminology when possible. For each AE, the investigator will evaluate and report the onset (date and time), resolution (date and time), intensity, causality, action taken, serious outcome (if applicable), and whether or not it caused the participant to discontinue the study.

Intensity will be assessed according to the following scale:

- Mild (awareness of sign or symptom, but easily tolerated)
- Moderate (discomfort sufficient to cause interference with normal activities)
- Severe (incapacitating, with inability to perform normal activities)

It is important to distinguish between serious and severe AEs. Severity is a measure of intensity whereas seriousness is defined by the criteria under Section [12.6.1.2](#). An AE of severe intensity may not be considered serious.

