12.5. Laboratory Assessments

Detailed instructions for blood sample collection are in the study manuals provided to study centers.

Local Laboratory Assessments:

The following clinical laboratory parameters will be assessed:

Blood Chemistry

Sodium	Total protein, serum	Total and indirect bilirubin
Potassium	Creatinine	Total cholesterol
Chloride	Blood urea nitrogen	Low-density lipoprotein
Carbon dioxide	AST	High-density lipoprotein
Calcium	ALT	Triglycerides
Glucose	Alkaline phosphatase	Uric acid
Albumin	Lactate dehydrogenase	CPK

Hematology

Hemoglobin	Differential:
Hematocrit	Neutrophils
Red blood cells	Lymphocytes
White blood cells	Monocytes
Red cell indices	Basophils
Platelet count	Eosinophils

Urinalysis

Microscopic analysis will only be done in the event of abnormal dipstick results.

Color	Glucose	Red blood cells
Clarity	Blood	Hyaline and other casts

pH	Bilirubin	Bacteria
Specific gravity	Leukocyte esterase	Epithelial cells
Ketones	Nitrite	Crystals
Protein	White blood cells	Yeast

Serological markers

HIV-1/2 antibodies	HBsAg	Hepatitis C virus antibodies
--------------------	-------	------------------------------

Other laboratory tests:

- Serum pregnancy tests will be performed for females of reproductive potential at screening, after which urine pregnancy tests will be performed.
- FSH testing will be performed at screening to confirm post-menopausal status in female participants who have had at least 12 months without menses.
- Coagulation testing (prothrombin time and partial thromboplastin time) will be performed as indicated in the Schedule of Events ([Table 3](#)). Samples for coagulation tests should be obtained before the procedures of endoscopy with esophageal biopsies are performed.

Abnormal laboratory values and laboratory AEs:

- All laboratory values must be reviewed by the investigator or authorized designee.
- Significantly abnormal tests must be repeated to confirm the nature and degree of the abnormality. When necessary, appropriate ancillary investigations should be initiated. If the abnormality fails to resolve or cannot be explained by events or conditions unrelated to the study treatment or its administration, the medical monitor must be consulted.
- The clinical significance of an abnormal test value, within the context of the disease under study, must be determined by the investigator.

Criteria for reporting laboratory values as an AE are provided in Section [12.6.1.4](#).

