7.8 Safety Analysis

The analysis of safety endpoint variables will include assessments of AEs, vital signs, 12-lead ECGs, physical examinations, and clinical laboratory tests. All Safety assessments will be summarized and tabulated as appropriate and will be listed by participant as applicable. All safety analyses will be performed on Safety Analysis Set. No formal statistical analysis will be performed on safety outcomes.

Example: The following variables will be evaluated to assess the safety:

- Adverse Events
- Clinical Laboratory Data
- 12 Lead Electrocardiogram (12-Lead ECG)
- Vital Sign measurements
- Physical Examination

Adverse Events:

Adverse Events will be coded using (MedDRA version 24.0 or latest) AE coding system for purpose of summary tables. Adverse events will be summarized using frequency count and percentage by MedDRA SOC and PT.

“Treatment-emergent” will be defined as starting or worsening after the first dose of investigational product. If the start date is missing, the event is assumed to be treatment emergent.

All AEs and TEAEs during the study will be summarized for the respective treatment group. A participant experiencing the same AEs and TEAEs multiple times will be counted only once for that PT. Similarly, if a participant experience multiple AEs and TEAEs (preferred terms) within the same SOC then that participant will be counted only once for that SOC. When summarizing by severity or relationship, only event with highest severity / relationship will be counted. Adverse events will be dichotomized into related (definitely, probably, and possibly) and unrelated (unlikely and not related) All AEs will be listed in chronological order of the events occurred.

An overview of AE summary will be presented. It will include the following:

- AEs
- Serious AEs
- TEAEs
- Serious TEAEs
- Treatment related TEAEs
- Treatment related Serious TEAEs
- TEAEs leading to study discontinuation
- TEAEs leading to death

The incidence and frequency of AEs will be summarized by treatment according to SOC and PT.

Treatment-Emergent Adverse Events (TEAEs)

A summary of the frequency (number and percentage of participants) of TEAEs will be presented by SOC, PT.

TEAEs will be summarized by treatment, system organ class, preferred term, and severity (mild, moderate, severe and undesirable, life-threatening or disabling and death).

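### Protocol Sections 12.6.3 and 12.6.1.4 disagree on when a non-serious laboratory, blood pressure or pulse change is an adverse event, so AE counts can depend on which section a site follows

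*Protocol*

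**What the plan says.** Protocol Section 12.6.3 (Recording Adverse Events) gives a general exemption: "Clinically significant changes in laboratory values, blood pressure, and pulse need not be reported as AEs". The next sentence sets the exceptions: "However, abnormal values that constitute an SAE or lead to discontinuation of administration of study treatment must be reported and recorded as an AE". The section does not mention Section 12.6.1.4.

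Protocol Section 12.6.1.4, whose title covers laboratory, vital-sign and ECG results, sets a different rule. It opens with "The criteria for determining whether an abnormal objective test finding should be reported as an AE include" and lists three alternatives:

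- The first concerns symptoms: "the test result is associated with accompanying symptoms; and/or"
- The second concerns work-up or intervention: "the test result requires additional diagnostic testing or medical/surgical intervention; and/or"
- The third concerns what follows from the finding: "the test result leads to discontinuation from the study, significant additional concomitant drug treatment, or other therapy"

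If an investigator wants to report a finding that meets none of these, the medical monitor is to be contacted. Repeating a test does not by itself make an AE.

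Protocol Section 12.5 contains a pointer for laboratory results only: "Criteria for reporting laboratory values as an AE are provided in Section" 12.6.1.4. Section 12.2 (Vital Signs) has no such pointer.

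SAP Section 7.8 takes the recorded events as they come: "All AEs and TEAEs during the study will be summarized for the respective treatment group". It has no rule on which abnormal values should be among them.

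**The concern.** Safety and tolerability is a secondary objective (Protocol Section 6.2). Safety is judged by clinical review of descriptive tables, without formal analysis (Section 15.3.3), so the AE counts carry much of the conclusion.

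The situation is a realistic one. The product is given as an IV bolus over 30 seconds (Section 9.1), and vital signs are taken 15 minutes afterwards (Section 12.2). Section 8.3.3 lists laboratory abnormalities that may delay a dose without ending treatment. Section 12.5 calls for ancillary investigations of significantly abnormal tests when necessary.

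Under Section 12.6.3, intensity, causality and action taken are rated for each AE. A finding that is not recorded as an AE gets none of these ratings. The planned tables do not replace them. SAP Section 7.8 tabulates clinical significance for ECGs and physical examinations. For laboratory values it plans descriptive statistics and out-of-range flags, and for vital signs descriptive statistics and listings. Protocol Section 15.3.3 promises a listing of markedly abnormal laboratory values to be defined in the SAP, but the SAP has no such definition.

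**Working it through.** The plan gives no figure to reproduce. The check is to apply both rules to each kind of finding, look for text that decides between them, and then put a scale on the result.

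**Step 1. Both rules applied to a laboratory value, blood pressure or pulse change.**

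| Finding | Section 12.6.3 | Section 12.6.1.4 | Result |
|---|---|---|---|
| 1. Serious | AE required | Nothing to the contrary | No conflict |
| 2. Not serious, study treatment stopped | AE required | Names leaving the study, not stopping treatment; AE if another criterion is met | No conflict, but the duty can rest on 12.6.3 alone |
| 3. Not serious, dosing continues, symptoms present | AE not required for the value | AE | Conflict |
| 4. Not serious, dosing continues, no symptoms, but worked up or treated | AE not required | AE | Conflict, in its clearest form |
| 5. Not serious, dosing continues, no symptoms, no action | AE not required | No criterion met; medical monitor contacted if the investigator still wants to report | No conflict |

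The disagreement is confined to rows 3 and 4. ECG results, temperature and respiratory rate are outside it, because the exemption in Section 12.6.3 does not name them.

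**Step 2. Is there text that decides between the rules?**

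- *Laboratory values:* Section 12.5 names Section 12.6.1.4 as the source of the criteria. That favors Section 12.6.1.4, although Section 12.6.3 still says otherwise.
- *Blood pressure and pulse:* no pointer was found in either document.
- *SAP Section 1:* its precedence clause covers differences in statistical analysis between the SAP and the protocol. It does not settle two protocol rules on what sites record.
- *Protocol Section 12.6.1.1:* it requires all AEs to be recorded, but does not say when an abnormal value is one.

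**Step 3. Scale.**

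- Inputs: about 36 randomized 1:1:1 (Protocol Section 9.3); about 15 centers (Synopsis).
- Participants per arm: 36 / 3 = 12.
- One participant counted or not counted for a given event: 1 / 12 = 8.3 percentage points of that arm's incidence.
- Randomized participants per center: 36 / 15 = 2.4.
- Expected number of row 3 and row 4 findings: not given. The total effect therefore cannot be computed, and 8.3 points is only the weight of one participant.

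**The case against.** The strongest reply is that the overlap is narrow and much of the information survives. Five points support it.

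- *Symptoms are still recorded.* Section 12.6.3 itself opens by requiring events that are volunteered, elicited or observed to be recorded, and Section 12.6.1.1 defines an AE as an undesirable medical condition. Dizziness with a fall in blood pressure is recordable under either section. This stands for row 3: the participant would normally be counted, and what may be lost is the blood pressure finding and its own ratings. It does not help in row 4, where there is no symptom.
- *Laboratory values are already directed.* This stands as far as Section 12.5 goes. It leaves blood pressure and pulse open.
- *The exemption is permissive.* This also stands. A site that reports satisfies both sections, so the right statement is that a site may omit the event, not that it will.
- *Assignment is central and blinded* (Sections 9.3 and 9.3.1). A site's reading of the protocol should not depend on the arm, so under-recording is expected to be non-differential.
- *Other records remain.* Section 15.3.3 lists laboratory results by participant, including unscheduled and repeat ones. SAP Section 7.8 lists vital signs individually. Section 9.2 records concomitant treatments with the reason for giving them. These keep the value and often the treatment, but not an AE term, intensity or causality.

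A reader might infer two stronger claims. One is that the arms become incomparable. The documents give no mechanism for a systematic difference; with about 2.4 participants per center, differing site practice can add chance imbalance, but nothing more is shown. The other is that a symptomatic, treated blood pressure fall would count as 8.3% of an arm under one section and 0% under the other. That fails because the symptoms would be recorded under Section 12.6.3 as well.

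**Conclusion.** The inconsistency is real and should be corrected. For non-serious laboratory, blood pressure and pulse changes in participants who continue dosing, Section 12.6.1.4 calls for an AE when there are symptoms, work-up or treatment, while Section 12.6.3 says none is needed. The clearest case is an asymptomatic change that is investigated or treated, and the least resolved measures are blood pressure and pulse.

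The consequence is AE under-counting that varies with site practice, together with missing causality and intensity ratings for the findings affected. Its size is unknown. The conclusion rests on two assumptions: that at least some sites rely on Section 12.6.3 as worded, and that such findings occur. It does not rest on any difference between arms, and none is expected.

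**What to change.** In Protocol Section 12.6.3, replace the sentence that exempts laboratory, blood pressure and pulse changes with: *Abnormal laboratory, vital sign and ECG results are reported as AEs according to the criteria in Section 12.6.1.4.*

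Keep the sentence after it, which requires abnormal values that are an SAE or lead to stopping study treatment to be recorded as AEs, and change its opening word from *However* to *In addition*. Deleting both sentences is tempting but would open a gap. Section 12.6.1.4 refers to leaving the study, whereas Sections 8.3.1 and 8.3.2 show that a participant can be taken off treatment for a laboratory value and remain in follow-up. Without symptoms, work-up or added therapy, such a value would meet no criterion in Section 12.6.1.4.

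The cost is a protocol wording change and a few more events recorded.

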12.6.4. Reporting Adverse Events

All SAEs (related and unrelated) will be recorded from the signing of consent form until 30 days following the end of treatment exposure. Any SAEs considered possibly or probably related to the investigational product and discovered by the investigator at any time after the study should be reported. All SAEs must be reported to the sponsor within 24 hours of the first awareness of the event. The investigator must complete, sign, and date the SAE pages, verify the accuracy of the information recorded on the SAE pages with the corresponding source documents, and send to the sponsor.

Additional follow-up information, if required or available, should all be reported to the sponsor within 24 hours of receipt and this should be completed on a follow-up SAE form and placed with the original SAE information and kept with the appropriate section of the eCRF and/or study file.

The sponsor is responsible for notifying the relevant regulatory authorities of certain events. It is the Principal Investigator's responsibility to notify the Institutional Review Board (IRB) or Independent Ethics Committee (IEC) of all SAEs that occur at his or her study center. Investigators will also be notified of all unexpected, serious, drug-related events (7/15 Day Safety Reports) that occur during the clinical study. Each study center is responsible for notifying its IRB or IEC of these additional SAEs.

All AEs that lead to a participant's withdrawal from the study must be reported to the sponsor's medical monitor within 30 days.

Refer to the study manuals for procedures to be followed.

13. ASSESSMENT OF PHARMACOKINETICS AND IMMUNOGENICITY

Samples will be collected pre- and postdose at the time points listed in the Schedule of Events ([Table 3](#)) for the following assessments:

- IRL201104 PK concentrations
- Antidrug antibodies (ADA)
- Immune cell phenotyping (T-subsets, B-subsets, and macrophage subsets)
- A20
- Serum cytokines
- Serum IgE/IgG4
- Serum EDN

Immunogenicity variables include ADA status. Results are reported as an optical density (OD) unit with a cut-off value. If the OD value is lower than the cut-off value, it is reported as negative, and if OD value is higher than the cut-off value it is positive. Participants who are assessed as ADA positive at their last study visit (early termination or end of study) will be considered for follow-up based on the overall clinical presentation at that time. Participants who are identified for follow-up may be asked to return to the clinic to have additional ADA samples collected for analysis.

The PK and immunogenicity assessments will be analyzed by a central laboratory.

14. RESEARCH SAMPLES

Research samples (blood/esophageal biopsies) will be collected at time points listed in the Schedule of Events ([Table 3](#)).

Use and Storage of Research Samples (Serum/Plasma/Esophageal Biopsies)

Research blood samples and esophageal biopsy samples will be banked and may be used to study the effects of the study treatment on target pathway modulation and EoE pathophysiology. Stored samples may also be used to discover markers predictive of IRL201104 response as well as identify markers associated with toxicity. Details for banking samples will be provided in the study manuals.

Technologies that may be employed include circulating protein marker analyses (eg, enzyme-linked-immunosorbent serologic assay, electrochemiluminescence), immunohistochemistry and/or histology of biopsies, and/or transcriptome analyses of blood and/or biopsy samples (eg, microarray, transcriptome sequencing, and/or quantitative reverse transcriptase-polymerase chain reaction).

Detailed instructions for sample collection and handling will be provided in the study manuals.

15. STATISTICS

15.1. General Considerations for Data Analysis

No formal statistical analysis will be conducted for this study. Summary statistics appropriate for categorical and continuous variables will be presented by treatment group and all inferences will be based on clinical evaluation of those results. A detailed statistical analysis plan (SAP) will be prepared that describes the method and style of the data summaries and listings for each endpoint.

15.2. Analysis Populations

15.2.1. Full Analysis Set

The full analysis set (FAS) will consist of all participants randomized at baseline who receive at least one dose of treatment.

This is the principal data set for the formal evaluation of the primary and secondary efficacy endpoints at Week 4. Participants will be evaluated based on the treatment group to which they were randomized.

